Study protocol**Material and Methods****1. Patient**

The Consolidated Standards of Reporting Trials (CONSORT) statement guidelines were followed in this single-center, prospective, parallel group, assessor-blinded, randomized controlled trial. All procedures were approved by the institutional review board of Police general hospital.

Patients who were diagnosed isolated closed fracture of distal end radius at Police General Hospital, Bangkok, Thailand between October 2021 and February 2023 were divided into the conventional group and the MIPO group at recruitment, using a computer-generated randomization program from www.randomizer.org. Patients were informed about the treatment options during a pre-interviewing session, and all eligible patients gave their written informed consent before the randomization and initialization of the allocated treatment. When patients arrived in the operating room, randomization took place using sealed envelopes containing assigned numbers. These envelopes were in the operating room and remained unopened until the patient's arrival. Neither the patient nor the attending physicians were informed about the randomization process. The orthopedic surgeon who assessed patient eligibility was not involved in randomization, thereby securing allocation concealment.

Inclusion criteria:

-We included those diagnosed with isolated closed fractures of the distal end radius requiring surgery,

-aged 18 years and older.

The Exclusion criteria were:

(1) Patients with bone fractures lasting more than 21 days

(2) open fractures

- (3) articular multifragmentary comminuted fractures of the distal radius categorized as AO/OTA 2R3C3
- (4) not suitable to undergo volar approach surgery
- (5) individuals with combined carpal fractures or dislocation
- (6) ulna fractures
- (7) associated injuries
- (8) a history of previous wrist surgery
- (9) diabetes mellitus
- (10) chronic wrist inflammation
- (11) wrist bone deformities
- (12) the use of anticoagulation drugs
- (13) uncooperative behavior
- (14) those refusing to participate in the research

2. Methods

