The primary outcome was measured using the pain visual analogue scale (VAS). Regarding the pain VAS, a score of 0 indicated no pain, and a score of 10 indicated the worst imaginable pain. The pain VAS score was recorded in the morning first 7 day then in the 2nd, 6th, 10th, 14th, and 24th weeks after surgery.

Patients attended outpatient department (OPD) follow-up appointments in the 2nd, 6th, 10th, 14th, and 24th weeks after surgery. The Quick Disabilities of the Arm, Shoulder, and Hand (Quick DASH) score indicated a functional outcome. The patient's satisfaction, along with the cosmetic score (rating the scar's appearance on a scale of 0 to 5, with 5 being excellent),. Hand grip strength was measured as a percentage of the strength in the other hand using a baseline hydraulic hand dynamometer with a JAMAR device (lbs force) from Sammons Preston, Inc., Bolingbrook, IL 60440-4989, in a 90 degree raised and extended arm position. The patient squeezed the dynamometer three times, and the highest score was recorded. Pinch strength was assessed by raising the patient's arm in front of them and bending it at a 90-degree angle, testing with a JAMAR Hydraulic Pinch Gauge. Three pinches on the device provided the highest score.

[figure not shown]
4 Statistical Analysis

IBM SPSS Statistics 27.0 was utilized for statistical analysis. Results were expressed as the mean \pm standard deviation. Statistically significant differences were determined based on $P < 0.05$ and the 95% confidence interval (CI). The Fisher's exact test was used to evaluate baseline characteristics including sex, fracture side, cause, AO/OTA type. The paired t-test was used to evaluate the age, incision length, VAS pain score, Quick DASH, functional outcomes (grip, pinch strength, range of motion), operative time, Aesthetics, Satisfaction and radiographic parameters. All subjects were analyzed and none of the subjects were lost to follow-up.

CONSORT diagram

[figure not shown]
Method

Data collection process

1) Pain Visual Analog Score

Pain Rating Scale – Wong-Baker FACES™ & Visual Analogue Scale (VAS)

Source:

Pain assessment in children undergoing venipuncture: The Wong-Baker faces scale versus skin conductance fluctuations - Scientific Figure on ResearchGate. Available from: https://www.researchgate.net/figure/Wong-Baker-Faces-TM-Pain-Rating-Scale-Reproduced-with-Permission-of-the-Wong-Baker-Faces_fig1_236604762 [accessed 12 Feb, 2020]

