This work by Department of Pharmacology and Pharmacy, HKU is licensed under a [Creative Commons Attribution-NonCommercial 3.0 Hong Kong License](https://creativecommons.org/licenses/by-nc/3.0/). Last updated Feb 2020.

Postoperative day	date	Pain VAS
0		
1		
2		
3		
4		
5		
6		
7		

2) QuickDASH form

QuickDASH

Please rate your ability to do the following activities in the last week by circling the number below the appropriate response.

	NO DIFFICULTY	MILD DIFFICULTY	MODERATE DIFFICULTY	SEVERE DIFFICULTY	UNABLE
1. Open a tight or new jar.	1	2	3	4	5
2. Do heavy household chores (e.g., wash walls, floors).	1	2	3	4	5
3. Carry a shopping bag or briefcase.	1	2	3	4	5
4. Wash your back.	1	2	3	4	5
5. Use a knife to cut food.	1	2	3	4	5
6. Recreational activities in which you take some force or impact through your arm, shoulder or hand (e.g., golf, hammering, tennis, etc.).	1	2	3	4	5

	NOT AT ALL	SLIGHTLY	MODERATELY	QUITE A BIT	EXTREMELY
7. During the past week, to what extent has your arm, shoulder or hand problem interfered with your normal social activities with family, friends, neighbours or groups?	1	2	3	4	5

	NOT LIMITED AT ALL	SLIGHTLY LIMITED	MODERATELY LIMITED	VERY LIMITED	UNABLE
8. During the past week, were you limited in your work or other regular daily activities as a result of your arm, shoulder or hand problem?	1	2	3	4	5

	NONE	MILD	MODERATE	SEVERE	EXTREME
9. Arm, shoulder or hand pain.	1	2	3	4	5
10. Tingling (pins and needles) in your arm, shoulder or hand.	1	2	3	4	5

	NO DIFFICULTY	MILD DIFFICULTY	MODERATE DIFFICULTY	SEVERE DIFFICULTY	SO MUCH DIFFICULTY THAT I CAN'T SLEEP
11. During the past week, how much difficulty have you had sleeping because of the pain in your arm, shoulder or hand? (circle number)	1	2	3	4	5

QuickDASH DISABILITY/SYMPOTM SCORE = $\left(\frac{\text{sum of } n \text{ responses}}{n} \right) - 1 \times 25$, where n is equal to the number of completed responses.

A QuickDASH score may not be calculated if there is greater than 1 missing item.

3) Table data collection

	MIPO	Conventional	p-value
Mean age, (SD); range			
Sex			
female			
male			
fracture side			
Dominant Hand			
Non-dominant Hand			
Cause			
fall			
road traffic accident			
sports			
AO/OTA 23			
A2			
A3			
B3			
C1			
C2			

	wk 2	wk 6	wk 10	wk 14	wk 24
(lbs)	F/U 1	F/U 2	F/U 3	F/U 4	F/U 5
Grip strength Fx					
Grip strength normal					
Pinch strength Fx					
Pinch strength normal					
ROM Fx					
Flexion					
Extension					
Supination					

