Pronation					
Radial deviation					
Ulnar deviation					
Pain (0-10)					
QuickDASH					
Wound size (mm)					
Cosmetic score					
Satisfy score					

	MIPO	Conventional	P-value
Pain score			
Q-DASH score			
Grip strength			
Subjective cosmetic			
Satisfaction			

Volar tilt	MIPO	Conventional	P-value
Initial			
Immediate post operation			
Final			

Radial inclination	MIPO	Conventional	P-value
Initial			
Immediate post operation			
Final			

Ulnar variance	MIPO	Conventional	P-value
Initial			
Immediate post operation			
Final			

patient	Pain (0-10)												mo	Q-DASH (0-100)						
	(no #)	Pre	D1	D2	D3	D4	D5	D6	D7	wk2	wk6	wk10	wk14	wk24	(mg)	Pre	wk2	wk6	wk10	wk14

patient	X-ray									Cos	Sat	Hand grip						
	RI			UV			VT					Hand grip						
	Pre	Post	F/U	Pre	Post	F/U	Pre	Post	F/U			wk2	wk6	wk10	wk14	wk24

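### The only test named for the primary pain VAS is a paired t-test, although the trial compares two independent randomised arms

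*Combined protocol and SAP*

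**What the plan says.** Section 1 (Patient) describes a "single-center, prospective, parallel group, assessor-blinded, randomized controlled trial". Its patients "were divided into the conventional group and the MIPO group at recruitment, using a computer-generated randomization program". No matching, matched-pair allocation or crossover is described, and the allocation ratio is not stated.

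Section 3 (Evaluation) makes pain the primary outcome: "The primary outcome was measured using the pain visual analogue scale (VAS"). It is measured repeatedly: "The pain VAS score was recorded in the morning first 7 day then in the 2nd, 6th, 10th, 14th, and 24th weeks after surgery".

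Section 4 (Statistical Analysis) names two tests. Fisher's exact test covers sex, fracture side, cause and AO/OTA type. For the continuous variables: "The paired t-test was used to evaluate the age, incision length, VAS pain score, Quick DASH, functional outcomes". The same sentence goes on to operative time, aesthetics, satisfaction and radiographic parameters. Significance rests on P < 0.05 and the 95% confidence interval. No independent-samples t-test, rank test or repeated-measures model appears.

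The blank tables under 3) Table data collection show which comparisons are meant. Age, the outcome scores and the radiographic parameters sit in tables with a MIPO column, a Conventional column and a p-value column.

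**The concern.** A paired t-test analyses differences within pairs, so it needs a rule that links each observation to one partner. In this trial the two arms are different people, and the plan gives no linking rule. Entered into a paired procedure, the arms would be matched by their position in the file.

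Three things would follow. The p-value and confidence interval would change with the sort order, so a second analyst holding the same data could not reproduce them. The degrees of freedom would fall from 2n − 2 to n − 1. If the arms were unequal, surplus patients would drop out of the calculation. This affects the primary outcome and every other continuous variable on the list, and it affects the two quantities on which section 4 bases significance.

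**Working it through.** **Step 1: can the sentence mean a within-patient comparison?** A before-and-after test would be a legitimate use of pairing, so this reading has to be excluded first.

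- Age has one value per patient, so there is nothing to pair. It is on the paired t-test list, and its row ("Mean age, (SD); range") lies in a table with MIPO, Conventional and p-value columns.
- Operative time is also on the list and also has one value per patient.
- In the volar tilt, radial inclination and ulnar variance tables, each time point, for example "Immediate post operation", has its own row and its own p-value across the two arms. That p-value compares arms, not times.
- Pain score, Q-DASH score, grip strength, cosmetic score and satisfaction are set out under the same three columns.

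The within-patient reading therefore fails. Where it is possible (pre versus post, or fractured versus normal hand), it would not test MIPO against conventional.

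**Step 2: what arbitrary pairing does.** The plan gives no figure to reproduce: the visible text has no sample size, SD, effect size or power. The figures below assume normal data, equal arms of n and a two-sided 5% level.

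Let r be the sample correlation between the two columns that a given row order happens to produce. With equal SDs in the arms, the mean difference is the same for both tests and

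- t(paired) = t(independent) / √(1 − r), on n − 1 instead of 2n − 2 degrees of freedom;
- CI width ratio = [t crit(n − 1) / t crit(2n − 2)] × √(1 − r).

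Over random row orders, r has mean 0 and SD 1/√(n − 1).

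*Example: n = 20, correct p exactly 0.05.* The critical values are 2.024 (38 df) and 2.093 (19 df). The paired test is significant only if 1 − r < (2.024/2.093)² = 0.935, that is, r > 0.065. The SD of r is 1/√19 = 0.229, so by a normal approximation this happens in about 39% of row orders. At r = ±1.96 × 0.229 = ±0.45, t(paired) is 2.024/√0.55 = 2.73 (p = 0.013) or 2.024/√1.45 = 1.68 (p = 0.109). The CI width ratio is 1.034 × √0.55 = 0.77 or 1.034 × √1.45 = 1.25.

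*Simulation.* Ten datasets were generated for each n and each correct (pooled two-sample) p, and each was re-paired 20,000 times. The results agree with the formula:

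| Correct p | Row orders with paired p < 0.05, n = 20 | n = 25 | n = 30 |
|---|---|---|---|
| 0.01 | 100% | 100% | 100% |
| 0.02 | 93.9% | 96.7% | 97.9% |
| 0.03 | 75.8% | 80.8% | 83.9% |
| 0.05 | 38.5% | 39.8% | 41.3% |
| 0.07 | 18.4% | 17.2% | 16.1% |
| 0.10 | 5.8% | 4.7% | 3.5% |
| 0.20 | 0.1% | 0.1% | 0.0% |

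At a correct p of 0.05, the central 95% of paired p-values is 0.015–0.106 (n = 20), 0.017–0.100 (n = 25) and 0.018–0.097 (n = 30). The central 95% of the CI width ratio is 0.78–1.24, 0.80–1.21 and 0.82–1.19, with medians of 1.02 to 1.03.

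**Step 3: error rates over repeated trials** (200,000 simulated trials per n, arbitrary row order):

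| n per arm | Type I error, paired | Power at d = 0.8, paired | Power, independent | Loss (points) |
|---|---|---|---|---|
| 10 | 5.00% | 35.9% | 39.6% | 3.7 |
| 20 | 4.94% | 67.1% | 69.4% | 2.3 |
| 25 | 5.07% | 77.4% | 79.2% | 1.8 |
| 30 | 4.91% | 84.8% | 86.1% | 1.3 |

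At 20 to 30 per arm, the two tests give different verdicts in 1.7–2.1% of trials with no effect and in 3.5–6.9% at d = 0.8.

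**The case against.** The best defence is that one word is wrong and nothing else. If the analyst ran the independent-samples procedure and wrote the wrong name, every result is reproducible and none changes. The layout gives this some support: the patient sheet has one row per patient with time points in columns, and a paired test between arms would need the arms side by side. The sheet's lack of a pair identifier proves little, because it shows no arm column either. Section 4 also says that all subjects were analysed, so the loss of surplus patients is a possibility only. The average effect is small: error rates barely move and few verdicts change.

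Most of this stands and limits the claim. High confidence attaches to the mismatch between test and design, not to any result being wrong. It does not remove the point. The documents do not say which procedure was run, and the analysis as written cannot be reproduced.

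A second objection is that a t-test at each time point means up to 12 tests of pain (days 1 to 7 and five later visits) with no primary time named. That multiplicity is already in the plan. Replacing the test neither creates nor cures it.

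**Conclusion.** The concern holds and must be fixed, because it affects the stated analysis of the primary outcome. The paired t-test does not fit a parallel-group trial with no described matching, and the plan's own tables exclude a within-patient reading.

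The likely numerical harm is narrow. Type I error stays near 5% and power falls by about 1 to 4 points for 10 to 30 per arm. Results with a correct p of 0.01 or less, or 0.20 or more, almost never change verdict. The exposure is to borderline results, with a correct p of about 0.02 to 0.10, and to interval width, which can be roughly 20% too narrow or too wide for any result.

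These sizes assume normal data, equal arms and arbitrary row order, and 20 to 30 per arm except for the error rates. The visible documents give no arm sizes, and the VAS is a bounded 0–10 score, so the figures are illustrative. The design mismatch does not depend on them.

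**What to change.** In section 4, replace the paired t-test with an independent-samples (Welch) t-test that reports the between-arm mean difference and its 95% confidence interval for each between-arm comparison. A pooled-variance test would also cure the mismatch. Add a statement of which SPSS procedure was actually run. If it was the paired procedure, re-run those results; if it was the independent-samples procedure, only the wording changes. ANCOVA on the pre-operative value, which the data sheet records for pain, Q-DASH and X-ray measures, is an optional gain in precision and is not needed to correct the error.

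The cost is one sentence and one statement of the procedure used, plus a re-run in the same software if needed. No new data or patients are required.

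### Pre-operative fields exist for pain, QuickDASH and three radiographic measures, but section 4 plans no between-arm comparison adjusted for them

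*Combined protocol and SAP*

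**What the plan says.** Section 4 names two procedures. Fisher's exact test covers sex, fracture side, cause and AO/OTA type. Everything continuous goes to one test: "The paired t-test was used to evaluate the age, incision length, VAS pain score, Quick DASH, functional outcomes", with operative time, aesthetics, satisfaction and radiographic parameters also on the list. It mentions no covariate, regression, mixed model or between-arm comparison of change.

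The per-patient sheet at the end of the document does provide baseline fields. The pain header begins "Pre D1 D2 D3 D4 D5 D6 D7", the QuickDASH header "Pre wk2 wk6 wk10 wk14", and the X-ray block for the three radiographic measures reads "Pre Post F/U Pre Post F/U Pre Post F/U".

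The text does not say when a Pre value is taken. In section 3 (Evaluation), "The pain VAS score was recorded in the morning first 7 day", followed by visits at weeks 2, 6, 10, 14 and 24. The pain diary covers postoperative days 0 to 7. Section 1 (Patient) places allocation late: "When patients arrived in the operating room, randomization took place using sealed envelopes containing assigned numbers".

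**The concern.** A baseline measurement of the outcome is often a useful covariate in a small two-arm trial. Adjusting for it can narrow the confidence interval, and it conditions the estimate on whatever imbalance chance produced in this particular randomisation. Here the sheet makes room for such measurements on the primary outcome and four others, and the analysis section makes no use of them in comparing the arms.

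This is a matter of efficiency. Under randomisation the unadjusted comparison is unbiased on average. What may be lost is power, and protection against a chance baseline gap carrying through to the estimated pain difference.

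**Working it through.** **Is any adjusted comparison planned?** There are two ways to read the paired t-test.

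1. *It means an independent-samples test.* The table shells support this, since each has a MIPO column, a Conventional column and a P-value. The comparison then uses unadjusted values. The radiographic shells put Initial, Immediate post operation and Final in separate rows, so the initial value gets its own comparison and does not adjust the final one. The pain and QuickDASH shells have a single row each and no baseline row.
2. *It means pre versus post within patients.* This would use the Pre values but would not compare the arms. It also cannot apply to age, incision length or operative time, which the same sentence lists and which have no paired value.

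Neither reading yields a baseline-adjusted difference between arms.

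**What could adjustment be worth?** The documents give no sample size, SD, effect size or correlation, so there is no trial figure to reproduce. Every input below is an assumption: n = 15, 20 or 30 per arm, standardised difference d = 0.8, two-sided alpha 0.05, and r from 0.1 to 0.5.

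- Unadjusted: noncentral t with df = 2n − 2 and noncentrality d√(n/2). At n = 20 this is 0.8 × √10 = 2.530 on 38 df, giving 69.3% power.
- ANCOVA: df = 2n − 3, with the noncentrality divided by √V, where V = (1 − r²)(1 + 1/(2n − 4)). The second factor is the cost of estimating the covariate slope. At n = 20 and r = 0.3, V = 0.91 × (1 + 1/36) = 0.935 and the noncentrality is 2.530/√0.935 = 2.616 on 37 df, giving 72.2%.

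| n per arm | Unadjusted | r = 0.1 | r = 0.2 | r = 0.3 | r = 0.5 |
|---|---|---|---|---|---|
| 15 | 56.2% | 54.9% | 56.2% | 58.4% | 66.8% |
| 20 | 69.3% | 68.5% | 69.9% | 72.2% | 80.1% |
| 30 | 86.1% | 85.9% | 86.9% | 88.6% | 93.6% |

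At 20 per arm, V is 1.0175, 0.987, 0.935 and 0.771 at r = 0.1, 0.2, 0.3 and 0.5. The variance of the arm difference therefore changes by about +1.7, −1.3, −6.5 and −22.9%. A simulation at 20 per arm agreed with the formula to within one percentage point of power.

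**Break-even.** Setting V = 1 gives r = √(1 − 1/(1 + 1/(2n − 4))), which is 0.19, 0.16 and 0.13 at 15, 20 and 30 per arm. Below that, adjustment slightly widens the interval.

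**Chance imbalance.** At 20 per arm, a baseline gap of the size exceeded in one trial in 20 is 1.96 × √(2/20) = 0.62 SD. With an assumed VAS SD of 2 at both times, the unadjusted difference in that trial would move by 0.62 × r × 2, which is 0.12, 0.25, 0.37 or 0.62 points at r = 0.1, 0.2, 0.3 or 0.5.

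**The case against.** The strongest reply is that this is a preference and not an error. Nothing in the documents promises adjustment, a blank column does not oblige anyone to use it, and an independent-samples comparison would be valid. The plain fault in the quoted sentence is the paired test for independent arms, and correcting its name repairs that without ANCOVA. It is right that validity is not at stake.

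The usefulness of the covariate is also uncertain, and this stands in full. The only evidence for Pre pain is a column header; its timing, the conditions of measurement and its completeness are unknown. The correlation may be low, because postoperative pain is scored under a fixed seven-day analgesic regimen with as-needed morphine. The QuickDASH form says "Please rate your ability to do the following activities in the last week", and fractures up to 21 days old are eligible, so for a recent fracture a Pre score may include days before the injury. At r = 0.3 or below the power change at 20 per arm runs from a loss of 0.8 points to a gain of 2.9. Only r = 0.5 gives a marked gain, and nothing in the documents supports that value. The 0.62-point shift combines r = 0.5 with an unusual imbalance and is not an expected effect.

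Finally, section 4 is in the past tense and states that "All subjects were analyzed and none of the subjects were lost to follow-up". If outcomes have been seen, adjustment can only be supplementary. That limits how the result may be presented, but it can still be reported.

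**Conclusion.** The point holds as an optional improvement. Five Pre fields exist, and on any reading section 4 plans no between-arm estimate adjusted for them, including for pain VAS. No bias follows from this.

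The plausible effect on power at 20 per arm and d = 0.8 runs from slightly negative (69.3% to 68.5% at r = 0.1) to useful (80.1% at r = 0.5). All of these inputs are assumed. The absence of adjustment is certain from the text; the benefit of adding it is not. It merits consideration mainly because the sentence on the paired test has to be rewritten anyway and the change is cheap.

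**What to change.** 1. State when Pre pain, QuickDASH and radiographic values are recorded, confirm that this is before the envelope is opened, and report how many are filled.
2. Name the primary pain time point. Section 3 lists 12: seven daily scores and five visits.
3. Replace the paired t-test with a between-group ANCOVA, or a mixed model across the repeated times: postoperative VAS on arm and Pre VAS; QuickDASH on arm and Pre QuickDASH; final radiographic value on arm and initial value. Report the adjusted difference with its 95% confidence interval.
4. If outcomes have already been seen, label the adjusted analysis post hoc and show it beside the unadjusted independent-samples comparison.

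The cost of ANCOVA is one degree of freedom per model, with a slight loss of precision if r is below about 0.16 with 40 patients in total. No new data are needed if the Pre fields were filled. If outcomes are unseen, only the analysis wording changes.
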